11.4. Recording Adverse Events

All AEs/SAEs experienced from the time of signed informed consent to the last follow-up will be recorded within each patient's eCRF. Information to be recorded should include: a concise description of the event; date and time of event onset and resolution; determination of seriousness, severity, corrective treatment, outcome, and relationship to IP or study procedure or underlying disease; and any action taken will be recorded. Resolution occurs when the patient has returned to his Baseline state of health or further improvement or worsening of the event is not expected.

Whenever possible, a diagnosis will be recorded as an AE, rather than symptoms or isolated laboratory abnormalities related to that diagnosis. Several symptoms or laboratory results that are related to the same diagnosis can thus be part of the same AE. A medical or surgical procedure is not an AE; rather the condition leading to the procedure should be recorded as the AE. Similarly, death is not an AE, but is rather the outcome of the AE(s) that resulted in death. If the AE(s) leading to death are not known, then death must be reported as an AE. All AEs will be followed until the resolution of AE, completion of the patient's study participation, or study termination, whichever occurs first. SAEs will be followed until resolution or until the condition stabilizes or returns to Baseline status.

11.5. Reporting Adverse Events

It is the responsibility of the Investigator that reporting is done adequately. To meet regulatory reporting timelines, the study site is obligated to report any SAE(s) to the Sponsor or designee immediately and no later than 24 hours after receiving information of an event that meets at least one of the criteria for seriousness as defined in Section [11.2.2](#).

11.6. Death

Death is an outcome of an event. All causes of death are SAEs. In the event of death, every effort should be made to obtain a death certificate and if possible, an autopsy report. If the cause of death is unknown, death will be recorded as the event.

11.7. Special Situations

11.7.1. Overdose

An overdose is defined as administration of a dose that is > 10% higher than the assigned dose per the protocol. An overdose is not an AE. An overdose will be reported even if it does not result in an AE. An overdose will be recorded on the appropriate form and sent to the Sponsor or designee within 24 hours.

11.7.2. Medication Error

A medication error is any preventable incident that may cause or lead to inappropriate study treatment use or patient harm, while the study drug is in the control of the health care

professional, or in certain cases, the patient. Such incidents may be due to health care professional practice, product labeling, packaging and preparation, procedures for administration, and systems, including the following: prescribing, order communication, dispensing, nomenclature, compounding, distribution, administration, education, monitoring, and use.

11.7.3. Accidental/Occupational Exposure

An accidental/occupational exposure is the unintentional exposure to a study treatment as a result of one's professional or nonprofessional occupation, or accidental exposure to a nonprofessional to whom exposure was not intended (eg, study drug given to wrong patient).

11.7.4. Pregnancy

If the female partner of a treated male subject becomes pregnant, the male subject must notify the Investigator within 24 hours of learning of the pregnancy. The Investigator must make every effort to ensure that the pregnant female is aware of the need to notify her healthcare provider regarding her male partner's participation in this clinical trial and his potential exposure to IP. The study site must complete a pregnancy form and send to the Sponsor or designee within 24 hours of learning of the pregnancy. The study site will make every effort to follow the pregnancy until outcome is known.

11.7.5. Reporting Special Situations

All occurrences of overdose, medication error, and accidental or occupational exposure with study treatment (regardless of whether an AE or SAE has occurred) must be reported on the designated special situations form as soon as possible. If the overdose, medication error, or accidental or occupational exposure is associated with an SAE, the SAE must be reported on an SAE Report Form within 24 hours.

11.7.6. Responsibilities of the Investigator

The responsibilities of the Investigator include, but are not limited to, the following:

- Monitoring and recording all AEs
- Determining seriousness, severity, and relationship to IP and/or study procedures and/or underlying disease
- Determining the onset and end date of each event
- Providing initial report of all SAEs within 24 hours of knowledge to the Sponsor or designee
- Providing follow-up information on SAEs in a timely and proactive manner
- Responding to queries regarding AEs and SAEs in a timely manner
- Ensuring that source documentation for all AEs is accurate and complete
- Ensuring that the study is conducted as defined in this protocol

11.7.7. Responsibilities of the Sponsor

The responsibilities of the Sponsor include, but are not limited to, the following:

- Training of Investigator and site staff on AE/SAE definitions, safety assessments, and site obligations related to safety monitoring and reporting of AE/SAEs
- Training with regard to the accurate and legal reporting of SAEs to all applicable regulatory bodies, IRBs/IECs, clinical trial sites, and other parties as appropriate and required within the regulated timing
- Safety monitoring and recording of AEs
- Adverse event processing and submission of expedited serious, unexpected, and related AEs to regulatory authorities per regulatory requirements
- Notification of expedited SAEs to sites
- Annual safety reporting to regulatory authorities and IRBs/IECs according to regional requirements

12. DATA COLLECTION, QUALITY ASSURANCE, AND MANAGEMENT

12.1. Recording of Data

Clinical data for this study will be captured in an electronic format. Electronic data capture will be provided by a contract research organization (CRO). The Investigator, or personnel delegated by the Investigator, will perform primary data collection/perform assessments based on the protocol design and record in source documentation. All required study information must be recorded on the appropriate eCRF screens/forms using the eCRF Completion Guidelines for the study. An eCRF must be completed for each patient that is enrolled. The study monitor will conduct 100% source data verification to ensure maximum data integrity. All data must be carefully entered in a timely fashion to permit meaningful interpretation and study oversight.

12.2. Quality Assurance

The eCRFs will be reviewed at regular intervals by a clinical monitor from the Sponsor or a representative of the Sponsor per the agreed-upon Monitoring Plan against the source documentation for identification and clarification of any discrepancies. Automated and manual quality checks will be in place to identify discrepancies, such as missing data, protocol deviations, out-of-range data, other data inconsistencies, and compliance. Requests for data clarification or correction will be documented as electronic queries within the eCRF and for the Investigator or study coordinator to resolve. All changes to the eCRFs will be tracked in an electronic audit trail. Site study files will be reviewed for compliance throughout the study.

Audits may be carried out by the Sponsor's representatives, and inspections may be performed by IRBs/IECs or regulatory authorities before, during, or after the study. The Investigator will allow and assist the Sponsor's representatives and any regulatory agency to have direct access to all study records, eCRFs, patient medical records and other source documentation, IP dispensing records and IP storage area, study facilities, and any other source documentation.

The Investigator must make study files and data accessible to the study monitor, to other authorized representatives of the Sponsor, and to the appropriate regulatory authority inspectors.

12.3. Retention of Study Documents

At study completion, all eCRF data for an individual site will be copied onto a compact disc and provided to the Investigator for retention in the study files. The supporting site study files must be retained by the Investigator for a period of 3 years after the investigation is discontinued and regulatory authorities are notified.

However, these documents should be retained for a longer period, if required by the applicable regulatory requirements or by an agreement with the Sponsor. No study documents will be destroyed or moved to a new location without prior written approval from the Sponsor. If the Investigator relocates, retires, or withdraws from the clinical study for any reason, all records that are required to be maintained for the study should be transferred to an agreed upon designee.

Patient records or other source data must be kept for the maximum period mandated by the hospital, institution, or private practice, but not less than 15 years.

If offsite archiving is used, all records should be retrieved and made available for review at the time of an audit or regulatory authority inspection.

13. STATISTICS

13.1. General Considerations

Details of the statistical methods for this study will be described in a Statistical Analysis Plan (SAP).

13.2. Analysis Endpoints

The study endpoints are listed in Section [7.3](#).

13.3. Determination of Sample Size

There is no formal sample size calculation. As this study is an OLE study of Study 4658-102, the sample size will be predicated on the sample size of Study 4658-102.

13.4. Analysis Sets

There will be one analysis population, the Safety Analysis Set, which includes all patients who are enrolled in the study and receive at least 1 dose of eteplirsen. This analysis set will be used for analyses of all endpoints, unless stated otherwise.

13.5. Disposition, Demographics, and Baseline Characteristics

The number and percentage of patients completing the study through Week 284 (ie, “completers”) or prematurely discontinuing before Week 284 will be summarized. Disposition will also be summarized over the entire 284-week duration of the study. Reasons for premature discontinuation will also be summarized.

Demographic characteristics will be summarized by age cohort and overall. Demographic data and Baseline characteristics will be presented in data listings.

13.6. Exposure

The cumulative exposure to eteplirsen, total volume of drug administered (mL), total number of infusions received, and cumulative amount of drug received will be summarized by age cohort and overall for all treated patients. Dosing information will be provided in a data listing.

13.7. Safety Analysis

Safety endpoints will be summarized for the Safety Analysis Set. All safety data will be presented in the data listings.

13.7.1. Adverse Events

Adverse events will be coded using the Medical Dictionary for Regulatory Activities (MedDRA) Version 20.1 or higher.

All AEs will be classified as either TEAEs or non-TEAEs. An AE will be considered a TEAE if it occurs at or after the start of study drug administration and within 4 weeks after the last study drug administration. An AE that does not meet the TEAE definition will be classified as a non-TEAE.

Treatment-emergent AEs will be summarized using the number and percentage of patients reporting AEs, by MedDRA system organ class (SOC) and preferred term (PT), for each dose

level and for the overall study population. The ordering of AEs will be based on the AE rate in the overall study population.

In general, summaries will have AEs categorized into all TEAEs and treatment-related TEAEs. Treatment-related TEAEs will be defined as those that the Investigator considers to be related to the study treatment (Section 11.3.1).

The following summary tables will be produced:

- TEAEs
- TEAEs by severity
- Treatment-related TEAEs
- Treatment-related TEAEs by severity
- SAEs
- AESIs
- AEs leading to study treatment discontinuation
- AEs leading to study withdrawal
- Deaths

The following listings will be produced:

- All TEAEs
- Non-TEAEs
- SAEs
- AESIs
- AEs leading to study treatment discontinuation
- AEs leading to study withdrawal
- Deaths and reasons for deaths

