Efficacy The efficacy of eteplirsen will be assessed by evaluating the change in NSAA scores from Baseline to the end of Week 144, Week 192, and Week 284.	
STATISTICAL METHODS:	
Sample Size As this study is an OLE study of Study 4658-102, the sample size will be predicated on the sample size of Study 4658-102.	
Safety Analyses Adverse events will be coded using the Medical Dictionary for Regulatory Activities (MedDRA) Version 20.1 or higher. An AE will be defined as a treatment-emergent adverse event (TEAE) if it developed or worsened in the period from the first dose of study drug to 28 days after the last dose of study drug. A treatment-related TEAE will be defined as a TEAE that the Investigator considered related to the study treatment.	

NAME OF COMPANY Sarepta Therapeutics, Inc. [name] [contact]	NAME OF FINISHED PRODUCT Eteplirsen Injection
	NAME OF ACTIVE INGREDIENT Eteplirsen

Congenital anomaly/birth defect: A congenital anomaly/birth defect that occurs in the offspring of a patient exposed to the investigational product.Important medical event: An AE that may not result in death, be life-threatening, or require hospitalization may be considered an SAE when, based upon appropriate medical judgment, the event may jeopardize the patient and may require medical or surgical intervention to prevent one of the outcomes listed above.	

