9.2. Treatments Administered

Eligible patients will receive a once weekly IV infusion of eteplirsen for up to 284 weeks. Eteplirsen should be prepared for dosing by following the steps detailed in the study-specific Pharmacy Manual.

Patients will receive the **ccc** mg/kg dose of eteplirsen while in this study. The period from Baseline through Week 284 will be considered the “Treatment Period.”

The following guidelines for the timing of dosing should be followed throughout the study:

- Patients should receive eteplirsen once every 7 days starting on Week 1. A window of ± 3 days from the scheduled dose is acceptable after the first infusion.
- Patients may not receive two (2) separate doses of eteplirsen within the same 60-hour period.
- The Medical Monitor should be contacted in the event of ≥ 2 consecutive missed doses.

Week 284 will be followed by a Safety Follow-up Period of up to 4 weeks. Patients may transition to commercially available product if commercially available eteplirsen is available. Home infusion of the study drug may be available.

The administered dose is calculated by patient weight, which will be collected on a weekly basis and used to calculate the dose to be administered at the next visit(s). For example, the weight collected at Week 2 will be used to calculate the doses to be infused during the Week 3 visit. Refer to the Pharmacy Manual for more details on dosing administration.

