11. ADVERSE EVENTS

11.1. Collection of Adverse Events

Over the entire duration of the study, study site personnel will ensure that all AEs are recorded appropriately. If an AE occurs, the primary concern is for patient safety, and the Investigator will use professional judgment and expertise to determine the appropriate course of action.

All AEs from the time of signed informed consent through the Safety Follow-up visit (which will occur approximately 4 weeks after the last infusion of eteplirsen, regardless of the patient's duration in the study) will be recorded in each individual patient's electronic case report form (eCRF). If at any time after the patient has completed participation in the study, the Investigator or study staff becomes aware of a SAE that the Investigator believes is related to the IP (Section 11.3.1) or is related to a study procedure (Section 11.3.2), then the event and any known details must be reported promptly to the Sponsor.

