11.2. Definition of Adverse Events

11.2.1. Adverse Event

An AE is any untoward medical occurrence in a clinical trial participant, which does not necessarily have a causal relationship with the investigational drug. An AE can, therefore, be any unfavorable and unintended symptom, sign, disease, condition, or test abnormality that occurs during or after administration of an IP, whether or not considered related to the IP.

Adverse events include:

- Symptoms described by the patient or signs observed by the Investigator or medical staff
- Test abnormalities (eg, laboratory tests, ECG, X-rays, etc.) that result in an alteration in medical care (diagnostic or therapeutic)

Abnormalities present at Baseline are considered AEs only if they re-occur after resolution or worsen during the AE collection period.

An AE will be defined as a treatment-emergent adverse event (TEAE) if it developed or worsened in the period from the first dose of study drug to 28 days after the last dose of study drug.

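### Section 13.7.1 drops worsening from the TEAE definition and splits the TEAE table by a dose level that has one category, where the synopsis asks for age cohort

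*Combined protocol and SAP*

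**What the plan says.** **Definition.** The protocol defines a treatment-emergent AE in three places.

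- Synopsis, Safety Analyses: "An AE will be defined as a treatment-emergent adverse event (TEAE) if it developed or worsened in the period from the first dose", with the window running to 28 days after the last dose.
- Section 11.2.1: the same test, "if it developed or worsened in the period from the first dose of study drug to 28 days after the last dose".
- Section 13.7.1: "An AE will be considered a TEAE if it occurs at or after the start of study drug administration and within 4 weeks" of the last administration. It then adds: "An AE that does not meet the TEAE definition will be classified as a non-TEAE".

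Two other statements set the reach of the difference. AE recording covers "All AEs from the time of signed informed consent through the Safety Follow-up visit", so it begins before dosing. Section 11.2.1 also says: "Abnormalities present at Baseline are considered AEs only if they re-occur after resolution or worsen during the AE collection period".

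**Layout.** The synopsis tabulates TEAEs, treatment-related TEAEs and treatment-emergent SAEs by SOC and PT for each age cohort and overall. It applies the same split to the maximum-severity tables for TEAEs and treatment-related TEAEs. Section 13.7.1 splits the TEAE table by dose level and overall. Sections 13.5 (demographics), 13.6 and 13.8 use age cohort and overall. Section 13.7.3 uses dose level. Section 11.2.1 gives no layout, so the layout conflict is between Section 13.7.1 and the synopsis.

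**The concern.** Safety is the primary objective and AE incidence is the first endpoint listed in Section 7.3.1, so the study needs one TEAE definition. Section 13.7.1 is the section that describes the AE tables, and it carries the narrower one. Two programmers, one working from Section 13.7.1 and one from Section 11.2.1, could classify the same worsened AE differently.

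The layout has a similar problem. A table built from Section 13.7.1 shows nothing beyond its overall column, and the age breakdown that the synopsis commits to does not appear in it.

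**Working it through.** The protocol has no formal sample size calculation (Section 13.3) and states no figure that bears on this point. The check is a comparison of texts with a little arithmetic.

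**1. Window.** 4 weeks × 7 days = 28 days. The three definitions share the same window, so the difference that matters is whether worsening counts.

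**2. Which events are classified differently.** The first dose is taken to mean the first dose in this extension study.

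| Event | Synopsis and 11.2.1 | 13.7.1 read literally |
|---|---|---|
| AE first arises within the window | TEAE | TEAE |
| Abnormality present at Baseline worsens on treatment, and the worsening is recorded as an AE | TEAE | TEAE, since that AE arises on treatment |
| AE starts after consent and before first dose, and its worsening is recorded as a new AE | TEAE | TEAE |
| AE starts after consent and before first dose, is kept as one record, and worsens on treatment | TEAE | **non-TEAE** |
| AE starts after consent and before first dose and does not worsen | non-TEAE | non-TEAE |

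One row differs. It can arise because recording starts at consent while dosing starts later: "Patients should receive eteplirsen once every 7 days starting on Week 1", and Week 1 follows the Baseline column in Table 2. The interval looks short, but the protocol does not state its length.

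**3. Tables affected.** Section 13.7.1 names 9 summary tables. Four are titled by TEAE: TEAEs, TEAEs by severity, treatment-related TEAEs, and treatment-related TEAEs by severity. The other 9 − 4 = 5 are named without that term. An affected AE would drop out of the four. It would remain in the listings, because Section 13.7 says: "All safety data will be presented in the data listings".

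**4. Weight of one patient.** Section 8.1 allows up to 15 patients. The smallest possible step in an overall percentage is 1/15 = 6.7 percentage points, and it is larger with fewer patients or within an age cohort. The step occurs in a PT row only if the patient has no other TEAE with that PT, because the synopsis counts repeats of a PT once per patient. The any-TEAE row moves only if the patient has no other TEAE at all.

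**5. Layout.** Sections 7.1, 7.2 and 9.2 assign one mg/kg dose to all patients. Its value is redacted, but no visible text assigns a second level in this study. Dose level therefore has 1 category, and its column equals the overall column. The synopsis specifies age cohort and overall for 3 SOC/PT summaries + 2 maximum-severity summaries = 5 AE summaries.

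**The case against.** Section 13.7.1 can be read as shorthand. Section 11.2.1 is the section on AE definitions, it gives the full test, and it already makes worsening of a Baseline abnormality an AE. Such an event arises on treatment and meets both texts. The remaining case needs an AE in the interval before dosing, kept as one record, that later worsens. Whether worsening goes into the same record or a new one depends on eCRF conventions that the protocol does not give. Nothing is lost, because the AE stays in the listings, and the listings of 15 patients can be read case by case. Section 13.1 defers statistical detail to a SAP, which may settle the matter.

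On layout, a duplicate column is redundant and changes no result. The synopsis commitment to age-cohort tables has not been withdrawn. No visible text defines the age cohorts, so changing the label does not by itself tell a programmer how to build the table. The 6.7-point step is the weight of any one patient in any row and is not evidence of an effect.

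Most of this stands as a limit on size. It does not make the texts agree. Section 13.7.1 expressly assigns everything outside its own wording to non-TEAE, and the protocol gives no order of precedence between synopsis and body. A SAP author would start from two definitions and two layouts. The missing cohort definition is a fair point. It affects Sections 13.5, 13.6 and 13.8 equally and is no reason to keep dose level.

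**Conclusion.** Both parts hold, and the point is minor. Read literally, Section 13.7.1 classes as non-TEAE an AE that began before dosing and worsened on treatment, which the synopsis and Section 11.2.1 class as a TEAE. It also specifies a dose-level column that duplicates the overall column in place of the age-cohort split in the synopsis.

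The number of AEs affected cannot be derived from the documents and is likely small. No effect on a safety conclusion has been shown. The definition part assumes that a worsened AE may be kept as one record. The layout part assumes that no redacted text assigns a second dose level. Whether a later SAP resolves either part cannot be checked here.

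**What to change.** Make two edits in Section 13.7.1:

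1. Replace the TEAE definition with the Section 11.2.1 wording: "if it developed or worsened in the period from the first dose of study drug to 28 days after the last dose".
2. Replace dose level with age cohort, keeping the overall column, as in the synopsis.

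For consistency, the second replacement could also be made in Section 13.7.3. The SAP should then state how the age cohorts are formed, because the visible text does not.

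The edits use terms already in the protocol and need no new data or assessments. TEAE counts may rise slightly, and percentages within small age cohorts will be coarse. The changes are best made before the SAP is written.
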